14.2.5. Safety Data

Unless otherwise specified, safety data will be summarized using descriptive statistics and individual safety data will be listed. AEs will be coded using the current version of the Medical Dictionary for Regulatory Activities, and incidence of treatment-emergent AEs will be presented by system organ class and preferred term. AE incidence rates will be described by cohort with and without regard to causality. The frequency of occurrence of overall toxicity, categorized by toxicity grades (NCI-CTCAE, current version) will be summarized. Change from baseline in clinical laboratory parameters, ECG, and vital signs will be summarized across time. Shift tables will be presented for selected laboratory parameters and vital signs. Physical examination results will be presented in listings.

14.2.6. Pharmacokinetic Data

Individual serum ACE-083 concentrations will be listed and summarized by treatment group. Listings will also include dosing times and actual sampling times relative to dosing. Individual and mean concentration data versus time will also be presented graphically. PK parameters of ACE-083 will be determined using the standard non-compartmental method. Individual PK parameters will be listed and will be summarized by treatment group.

14.2.7. Anti-drug Antibody Data

Individual ADA data will be listed. The results of ADA testing for ACE-083 over time as well as results following further characterization of positive ADA samples will also be presented. Exploratory analysis will be performed on the potential effect of ADA on ACE-083 PK exposure if ADA tests are determined to be positive.

14.3. Determination of Sample Size

There was no formal sample size calculation for Part 1 or Part 2 of this study.

The sample size for Part 1 is determined by how many subjects from Part 1 of Studies A083-02 and A083-03 decide to participate in this study. Similarly, the sample size for Part 2 is based upon how many subjects from Part 2 of Studies A083-02 and A083-03 and Part 1 of this study participate in Part 2 of this study.

Non-inferiority of the q8w or q4w maintenance dose regimen during the first 6 months of the maintenance phase for the percent change in total muscle volume relative to the start of the maintenance phase (or equivalently the end of the loading phase – either from Part 2 of phase 2 studies A083-02 and A083-03 or from Part 1 of this study) will be analyzed.

Based on data from Parts 1 of Studies A083-02 and A083-03, it is assumed that the standard deviation is approximately 9. A non-inferiority margin of -5 and a 0.05 significance level is used. If 75 subjects per maintenance regimen participate and the observed mean percent change in total muscle volume at the first 6 months of the maintenance regimen from the start of the maintenance regimen is -2, the probability to conclude that the effect of any single maintenance regimen (q8w or q4w) is non-inferior is approximately 89%. If 65 subjects per maintenance regimen participate and the observed mean percent change is -2, the probability to conclude that the effect of any single maintenance regimen (q8w or q4w) is non-inferior is approximately 85%. If 57 subjects per maintenance regimen participate, the probability is approximately 80%.

Clinical Study Protocol ACE-083 Study A083-04

Revision: 00

14.4. Interim Analysis

Periodic reviews of the available safety and tolerability will be planned and reported to the SRT in accordance with the SRT charter. During the course of Part 2, an interim analysis may be performed when some or all subjects have completed 6 months post start of the maintenance phase in order to assess adequacy of dosing regimens in this study and to plan for future studies with ACE-083. Details will be described in the Statistical Analysis Plan.

14.5. Deviation from Original Analysis Plan

A formal statistical analysis plan for the analysis and presentation of data from this study will be prepared before the database lock. Deviations from the statistical analyses outlined in this protocol will be indicated in this plan; any further modifications will be noted in the final clinical study report.

15. ETHICS

15.1. Institutional Review Board

The investigator will submit this protocol, any protocol modifications, and the patient ICF to be used in this study to the appropriate IRB/IEC for review and approval. A letter confirming IRB/IEC approval of the protocol and ICF as well as a statement that the IRB/IEC is organized and operates according to GCP and the applicable laws and regulations, must be forwarded to the sponsor prior to the enrollment of patients into the study. A copy of the approved ICF will also be forwarded to the sponsor. Appropriate reports on the progress of the study will be made to the IEC and the sponsor by the principal investigator in accordance with applicable governmental regulations and in agreement with the policy established by the sponsor.

15.2. Ethical Conduct of the Study

The sponsor and the investigator must comply with all instructions, regulations, and agreements in this protocol and in the applicable ICH and GCP guidelines, and must also conduct the study in accordance with local regulations.

15.3. Subject Information and Consent

Informed written consent is required from each subject prior to any testing under this protocol, including screening tests and evaluations. The ICF, as specified by the study center's IEC, must follow the Protection of Human Patients regulations listed in the Code of Federal Regulations, Title 21, Part 50. The principles of informed consent in the Declaration of Helsinki should be implemented in this clinical study and should comply with local and national regulations. The consent forms must be in a language fully comprehensible to the prospective subject. Information should be given in both oral and written form whenever possible and deemed appropriate by the IEC.

The background of the proposed study and the benefits and risks of the procedures and study must be explained to the subjects. It is the responsibility of the investigator to obtain consent and to provide the subject with a copy of the signed and dated ICF. Confirmation of a subject's informed consent must also be documented in the subject's medical record prior to any testing under this protocol, including screening tests and evaluations.

All ICFs used in this study must be approved by the appropriate IEC and by the sponsor or designee. The ICF must not be altered without the prior agreement of the relevant IEC and the sponsor.

15.4. Subject Data Protection

Prior to any testing under this protocol, including screening tests and evaluations, subjects must authorize the release and use of protected health information, as required by local law.

The subject will not be identified by name in the CRF or in any study reports. These reports will be used for research purposes only. The sponsor, its designee, and various government health agencies may inspect the records of this study. Every effort will be made to keep the patient's personal medical data confidential.

16. SOURCE DOCUMENTATION AND INVESTIGATOR FILES

16.1. Study Monitoring

The clinical monitor will arrange to visit the clinical sites at regular intervals during the study. The monitoring visits must be conducted according to the applicable ICH and GCP guidelines to ensure protocol adherence, quality of data, drug accountability, compliance with regulatory requirements, and continued adequacy of the clinical sites and their facilities. During these visits, CRFs and other data related to the study will be reviewed and any discrepancies or omissions will be resolved. The clinical monitor will be given access to study-relevant source documents (including medical records) for purposes of source data verification.

16.2. Audits and Inspections

The investigators and clinical sites will permit trial-related monitoring, audits, IEC review, and regulatory inspections as requested by FDA or other health authorities and the sponsor or designee. In addition to CRFs, the clinical site will permit direct access to source data/documents (i.e., original medical records, laboratory reports, hospital documents, progress reports, signed ICFs, etc.). During and/or after completion of the study, quality assurance officers named by the sponsor or the regulatory authorities may wish to perform on-site audits. The investigator is expected to cooperate with any audit and provide assistance and documentation (including source data) as requested.

17. QUALITY CONTROL AND QUALITY ASSURANCE

17.1. Data Quality Control and Quality Assurance

17.1.1. Investigator Responsibility

The investigator is responsible for ensuring the study is conducted according to the protocol, Code of Federal Regulations, GCP, and applicable regulatory requirements. The investigator's responsibilities are outlined in these documents and must include the responsibility to obtain a signed informed consent prior to patient participation in the study.

17.1.2. Protocol Modifications

The investigator should not modify the protocol without agreement from the sponsor and prior review or approval by the IEC/IRB, unless an emergency situation requires protocol modification to ensure the safety of patients. Any deviations from the protocol should be documented by the investigator or designee.

18. CONFIDENTIALITY

To maintain patient privacy, all CRFs, study drug accountability records, study reports and communications will identify the patient by the assigned subject identification number. The investigator will grant clinical monitor(s) and auditor(s) from the sponsor or designee and regulatory authorities' access to the patient's original medical records for verification of data gathered on the CRFs and to audit the data collection process. The subject's confidentiality will be maintained and will not be made publicly available. The subject's medical information will only be released to the extent permitted by the applicable laws and regulations.

All information regarding the investigational product supplied by the sponsor to the investigator is privileged and confidential information. The investigator agrees to use this information to accomplish the study and will not use it for other purposes without consent from the sponsor. It is understood that there is an obligation to provide the sponsor with complete data obtained during the study. The information obtained from the clinical study will be used towards the development of the investigational product and may be disclosed to regulatory authorities, other investigators, corporate partners, or consultants as required.

19. PUBLICATION POLICY

All information concerning study drug is considered confidential and shall remain the sole property of the sponsor. The investigator(s) agrees to use this information only in conducting the study and shall not use it for any other purposes without the sponsor's written approval. The investigator(s) agrees not to disclose the sponsor's confidential information to anyone except to persons involved in the study that need such information to assist in conducting the study, and then only on like terms of confidentiality and non-use.

It is understood by the investigator(s) that the information developed from this clinical study will be used by the sponsor in connection with the development of study drug, and therefore may be disclosed as required to regulatory agencies. To allow for the use of the information derived from clinical studies, it is understood that there is an obligation to provide the sponsor with complete test results and all data developed in the study.

No publication or disclosure of study results will be permitted except as specified in a separate, written, agreement between the sponsor and the investigator(s).

ACE-083

20. PROTOCOL AMENDMENTS

Protocol amendments that impact patient safety, change the scope of the investigation, or affect the scientific quality of the study must be approved by the IEC/IRB and submitted to the appropriate regulatory authorities before implementation.

In the event that the protocol needs to be modified immediately to eliminate an apparent hazard to a patient, the sponsor will implement the protocol change and subsequently amend the protocol and notify the regulatory authorities and/or the IEC/IRB, as appropriate.

21. DATA HANDLING AND RECORDKEEPING

21.1. Case Report Form Completion

CRFs will be completed for each enrolled subject. It is the investigator's responsibility to ensure the accuracy, completeness, and timeliness of the data reported in the subject's CRF. Source documentation supporting the CRF data should indicate the subject's participation in the study and should document the dates and details of study procedures, AEs, and patient status.

Investigators will maintain copies of the CRFs at the clinical site. For subjects who discontinue or terminate from the study, the CRFs will be completed as much as possible, and the reason for the discontinuation or termination clearly and concisely specified on the appropriate CRF.

21.2. Retention of Records

The investigator will maintain all study records according to ICH GCP and applicable regulatory requirements. Records will be retained for at least 2 years after the last marketing application approval or 2 years after formal discontinuation of the clinical development of the investigational product, or according to applicable regulatory requirements. If the investigator withdraws from the responsibility of keeping the study records, custody must be transferred to a person willing to accept the responsibility. The sponsor must be notified in writing if a custodial change occurs.

23. APPENDICES

ACE-083

APPENDIX 1. SCHEDULE OF EVENTS

Table 8: Schedule of Events for Part 1: Loading Phase

	Screening	Part 1: Loading Phase*										
Dose	-	L1	L2	L3	L4	L5	L6					
Planned Day	-28 to -1	1	29 ± 3d	57 ± 3d	85 ± 3d	113 ± 3d	141 ± 3d					
Informed Consent	X											
Inclusion/exclusion criteria	X											
Urine pregnancy test		X		X		X						
Medical History	X											
MMT assessment (MRC)	X	X			X							
Full Physical examination ²	X											
Limited Physical examination ²		X			X							
Injection site examination		X	X	X	X	X	X					
Vital signs ³	X	X	X	X	X	X	X					
Hematology	X	X		X		X						
Chemistry	X	X		X		X						
Urinalysis		X		X		X						
Biomarkers		X			X							
Anti-drug antibody	X	X		X		X						
Serum PK ⁶		0,1, 2, 4, 24 h			0,1, 2, 4, 24 h	X	X					
ECG (12 lead) ⁷	X	X			X							
Bilateral MRI ⁴		X			X							
10MWR, 6MWT, 100mTT (all TA subjects); 4-stair climb (FSHD TA subjects); PUL (FSHD BB subjects) ⁵	X	X			X							
QMT assessment (MVIC by hand-held dynamometer)	X	X			X							
FSHD-HI or CMT-HI	X	X			X							
Monitoring of concomitant medications	X	X	X	X	X	X	X					
Monitoring of adverse events	X	X	X	X	X	X	X					
Study drug administration ¹		X	X	X	X	X	X					

^{*}The L before the Dose in this table denotes that these doses occur in the Loading Phase.

¹ Study procedures must be done prior to administration of study drug. Reference the Study Manual for the order of study procedures. All visit-day windows should be considered relative to the date of the previous dose of ACE-083. Actual visit days (e.g. Day 29, Day 57) may be different than planned due to windows on visits and dosing delays.

² Full physical examination during the screening period; limited physical examination for Days 1, 85.

³ Vital signs (weight, heart rate, systolic and diastolic blood pressure) must be taken prior to administration of study drug on dosing days

⁴MRI should be completed within 5 days prior to scheduled dose administration, with the exception of the Day 1 MRI, which may be completed within 14 days prior to the Day 1 visit. If performed on the same day as study drug administration, the subject should receive the MRI first.

⁵ These function tests may be performed within 3 days prior to Day 1 visit.

⁶ PK samples on dosing day have a ±15 minute window with the exception of the 24 h time point, which has a ± 2 window. Pre-dose samples may be collected up to 4 h prior to dosing.

 $^{^{7}}$ ECG to be conducted ± 1 hour of the 4h PK sample

Table 9: Schedule of Events for Maintenance Phase and Follow-up: q4w dosing arm

	Part 2: Maintenance Phase								Follow-	Follow-up Visits				
Planned Day(s)	1 ± 3d	29 ± 3d	57 ± 3d	85 ± d	113 ± 3d	141 ± 3d	169 ± 3d	197-309 ± 3d	337 ± 3d	365-477 ± 3d	505 ± 3d	533-645 ± 3d	ET 673	EOS 701
Dose number (q4w)	1	2	3	4	5	6	7	8-12	13	14-18	19	20-24	$\pm 5d$	$\pm 5d$
Study Drug Administration ¹	X	X	X	X	X	X	X	X	X	X	X	X		
Informed consent	X													
Urine pregnancy test	X		X		X		X		X		X		X	
MMT assessment (MRC)	X				X		X		X		X		X	X
Limited physical examination ²	X				X		X		X		X			X
Injection site examination	X	X	X	X	X	X	X	X	X	X	X	X	X	
Vital signs ³	X	X	X	X	X	X	X	X	X	X	X	X	X	
Hematology	X				X		X		X		X		X	
Chemistry	X				X		X		X		X		X	
Urinalysis	X				X		X		X		X		X	
Biomarkers	X				X		X		X		X		X	X
Anti-drug antibody	X				X		X		X		X		X	X
ECG (12 lead)	X				X		X		X		X		X	
Bilateral MRI ⁴	X				X		X		X		X		X	
10MWR, 6MWT, 100mTT (all TA subjects); 4-stair climb (FSHD TA subjects); PUL (FSHD BB subjects) ⁵	X				X		X		X		X		X	X
QMT assessment (MVIC by hand-held dynamometer)	X				X		X		X		X		X	X
CMT-HI/FSHD-HI	X				X		X		X		X		X	X
Concomitant medications	X	X	X	X	X	X	X	X	X	X	X	X	X	X
Adverse events	X	X	X	X	X	X	X	X	X	X	X	X	X	X

¹ Study procedures must be done prior to administration of study drug. Reference the Study Manual for the order of study procedures. For subjects who enroll in A083-04 without treatment interruption, the Day 1 Dose 1 (D1D1) visit may coincide with the ET visit of the base study (either A083-032 or A083-03). For these subjects without treatment interruption, the D1D1 procedures shaded in grey may be conducted as part of the ET visit for Study A083-02 or A083-03 and may not need to be repeated for study A083-04.

Visit schedule: All visit-day windows should be considered relative to the date of the previous dose of ACE-083. Actual visit days (e.g. Day 29, Day 57, Day 85) may be different than planned due to windows on visits and potential dosing delays.

² Limited physical examination (skin, cardiovascular, respiratory, musculoskeletal, and neurological assessments) only.

³ Vital signs (weight, heart rate, systolic and diastolic blood pressure) must be taken prior to administration of study drug on dosing days

⁴MRI assessments should be completed within 5 days prior to scheduled dose administration, with the exception of the Day 1 MRI, which may be completed within 14 days prior to the Day 1 visit. If performed on the same day as study drug administration, the subject should receive the MRI first. MRI assessments during the follow-up period have a ± 5-day window.

⁵ These function tests may be performed within 3 days prior to Day 1 visit.

Table 10: Schedule of Events for Maintenance Phase and Follow-up: q8w dosing arm

	Part 2: Maintenance Phase								Follow-up Visits					
Planned Day(s)	1	57 ± 5d	113 ± 5d	169 ± 5d	225 ± 5d	281 ± 5d	337 ± 5d	393 ± 5d	449 ± 5d	505 ± 5d	561 ± 5d	617 ± 5d	ET 673	EOS 701
Dose number (q8w)	1	2	3	4	5	6	7	8	9	10	11	12	± 5d	± 5d
Study Drug Administration ¹	X	X	X	X	X	X	X	X	X	X	X	X		
Informed consent	X													
Urine pregnancy test	X	X	X	X			X			X				
MMT assessment (MRC)	X		X	X			X			X			X	X
Limited physical examination ²	X		X	X			X			X			X	X
Injection site examination	X	X	X	X	X	X	X	X	X	X	X	X		
Vital signs ³	X	X	X	X	X	X	X	X	X	X	X	X	X	
Hematology	X		X	X			X			X			X	
Chemistry	X		X	X			X			X			X	
Urinalysis	X		X	X			X			X			X	
Biomarkers	X		X	X			X			X			X	X
Anti-drug antibody	X		X	X			X			X			X	X
ECG (12 lead)	X		X	X			X			X			X	
Bilateral MRI ⁴	X		X	X			X			X			X	
10MWR, 6MWT, 100mTT (all TA subjects); 4-stair climb (FSHD TA subjects); PUL (FSHD BB subjects) ⁵	X		X	X			X			X			X	X
QMT assessment (MVIC by hand-held dynamometer)	X		X	X			X			X			X	X
CMT-HI/FSHD-HI	X		X	X			X			X			X	X
Concomitant medications	X	X	X	X	X	X	X	X	X	X	X	X	X	X
Adverse events	X	X	X	X	X	X	X	X	X	X	X	X	X	X

¹Study procedures must be done prior to administration of study drug. Reference the Study Manual for the order of study procedures. For subjects who enroll in A083-04 without treatment interruption, the Day 1 Dose 1 (D1D1) visit may coincide with the ET visit of the base study (either A083-032 or A083-03). For these subjects without treatment interruption, the D1D1 procedures shaded in grey may be conducted as part of the ET visit for Study A083-02 or A083-03 and may not need to be repeated for study A083-04.

Visit schedule: All visit-day windows should be considered relative to the date of the previous dose of ACE-083. Actual visit days (e.g. Day 29, Day 57, Day 113) may be different than planned due to windows on visits and potential dosing delays.

² Limited physical examination (skin, cardiovascular, respiratory, musculoskeletal, and neurological assessments) only.

³ Vital signs (weight, heart rate, systolic and diastolic blood pressure) must be taken prior to administration of study drug on dosing days

⁴ MRI assessments should be completed within 5 days prior to scheduled dose administration, with the exception of the Day 1 MRI, which may be completed within 14 days prior to the Day 1 visit. If performed on the same day as study drug administration, the subject should receive the MRI first. MRI assessments during the follow-up period have a ± 5-day window.

⁵ These function tests may be performed within 3 days prior to Day 1 visit.

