9. DISCONTINUATION / WITHDRAWAL CRITERIA

The reasons for treatment discontinuation / study withdrawal must be recorded in the patient's case report form (CRF). The investigator must notify the sponsor and medical monitor when a patient has been withdrawn from the study.

All patients who are withdrawn from the study prior to the end of treatment (EOT) visit should complete the tests and evaluations (excluding the MRI if it has been done within 4 weeks of study withdrawal) scheduled for the EOT visit (Day 673) at the time of withdrawal and will be asked to return to the clinic to complete the remaining follow-up visit assessment.

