12.2. Study Assessments

For each subject, all study procedures should be conducted according to the Schedule of Events (Appendix 1) and following the study-specific recommendations included in the Study Manual.

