13.5. Reporting Adverse Events

As described in Section 13.4, all AEs must be recorded in the CRF up until the last follow-up visit. All subjects who received at least one dose of study drug, whether they completed the treatment period or not, should complete the end of treatment procedures.

All AEs will be followed until clinical database lock (or resolution if it occurs before database lock). All SAEs will undergo active follow-up until the event(s) have returned to baseline status, have stabilized, or until the investigator and sponsor have agreed that follow-up is no longer necessary. Follow-up data for SAEs obtained after clinical database lock will be incorporated into the study drug safety database. If a subject experiences an SAE that is considered to be related to study treatment at any time after the study, it must be reported to the sponsor.

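### Minor: the end-of-treatment visit (Day 673) carries a different safety set in each maintenance arm, with no reason given

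*Protocol*

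**What the plan says.** Protocol Section 12.2 sends sites to the schedules: "all study procedures should be conducted according to the Schedule of Events (Appendix 1) and following the study-specific recommendations included in the Study Manual". For the maintenance phase there are two, "Table 9: Schedule of Events for Maintenance Phase and Follow-up: q4w dosing arm" and "Table 10: Schedule of Events for Maintenance Phase and Follow-up: q8w dosing arm". Both end with ET on Day 673 and EOS on Day 701.

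In the ET column, Table 9 marks the injection-site examination and the urine pregnancy test and leaves the limited physical examination blank. Table 10 does the reverse on all three rows. Both tables mark the limited physical examination at EOS, and neither marks the other two there.

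Footnote 1 to both tables fixes the order on dosing days: "Study procedures must be done prior to administration of study drug". The only footnote attached to any of the three rows describes content: "Limited physical examination (skin, cardiovascular, respiratory, musculoskeletal, and neurological assessments) only".

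The ET set is not confined to completers. Section 9 has withdrawing patients complete the tests "scheduled for the EOT visit (Day 673) at the time of withdrawal" and adds that they "will be asked to return to the clinic to complete the remaining follow-up visit assessment". Section 13.5 says that all dosed subjects, "whether they completed the treatment period or not, should complete the end of treatment procedures".

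**The concern.** The two arms receive the same drug at the same dose into the same muscles and share an ET day, yet their exit safety checks differ in three cells. The differences run in both directions, so this is not a lighter schedule chosen for the arm with fewer doses. It looks like a drafting slip.

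The stake is patient safety at exit. Because examinations and tests come before the injection at each visit, the last injection is followed only by what ET and EOS list. In q8w that means no dedicated look at the last injection site and no pregnancy test, whether the subject completes or withdraws. The early withdrawal matters most, because exit may come days after an injection. A positive test would trigger sponsor notification within 24 hours and monitoring to the end of the pregnancy (Section 13.6). Injection-site reactions are also part of the primary safety endpoint (Section 6), and an ET site check in one arm only makes ascertainment at exit unequal in an open-label comparison of regimens.

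**Working it through.** The protocol states no figure on this point, so the check compares the two tables cell by cell and then counts days.

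**Alignment.** The three rows in question, and the others that were split, have 14 visit cells in both tables, so there is no sign of a shifted column.

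**Cells at exit.**

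| Row | q4w ET | q8w ET | q4w EOS | q8w EOS |
|---|---|---|---|---|
| Urine pregnancy test | X | blank | blank | blank |
| Injection-site examination | X | blank | blank | blank |
| Limited physical examination | blank | X | X | X |

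Every other row has the same ET entry in both tables, and the EOS columns are identical.

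**Planned doses** (Tables 9 and 10).
- q4w: Day 1 + 28i, i = 0 to 23; the last is 1 + 28 × 23 = Day 645.
- q8w: Day 1 + 56i, i = 0 to 11; the last is 1 + 56 × 11 = Day 617.
- ET minus last dose: 673 − 645 = 28 days (q4w); 673 − 617 = 56 days (q8w).

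**Injection-site examination, completers.** It is listed at every dosing visit in both arms, before the injection, so each dose is checked at the next visit. In q4w the Day 645 dose is checked at ET: 0 of 24 doses are left without a later examination. In q8w nothing follows the Day 617 dose: 1 of 12.

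**Urine pregnancy test, completers.** q4w tests fall on Days 1, 57, 113, 169, 337, 505 and 673; q8w tests fall on the first six of these only. Tests precede dosing, so the q8w doses with no later test are Days 505, 561 and 617: 3 of 12. In q4w it is 0 of 24. The last q8w test is 673 − 505 = 168 days before ET.

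**Urine pregnancy test, early q8w withdrawal.** Age of the last test if the subject leaves after a given dose, up to and including the next planned visit:

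| Last dose on Day | Last test on Day | Age on dose day | Age at next planned visit (+56) |
|---|---|---|---|
| 1, 57, 113, 169, 337, 505 | same day | 0 | 56 |
| 225, 393, 561 | 169, 337, 505 | 56 | 112 |
| 281, 449, 617 | 169, 337, 505 | 112 | 168 |

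A q4w subject who withdraws is tested at the ET assessment instead.

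**Limited physical examination.** q4w: Days 1, 113, 169, 337, 505 and 701. q8w: the same days plus 673. The q4w examination comes 701 − 673 = 28 days later.

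**Does the dosing interval explain it?** No. From Day 57 to Day 617 the q8w site is examined 56 days after the previous injection; an ET check would be the same 56 days after the last one. The 8-week post-dose period for contraception and pregnancy reporting ends for a q8w completer on 617 + 56 = Day 673, the day on which the test is blank. Nor does the interval explain the missing q4w physical examination.

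**The case against.** The strongest reply is that nothing here is contradictory. Each arm has its own table, no sentence requires the ET sets to match, and Section 12.2 also refers to a Study Manual that is not available. This stands in part: it is a matter of schedule design. But both arms leave through the same visit, and the protocol offers no reason for the differences.

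Second, the last q8w site is not unwatched. The limited physical examination at ET and EOS covers skin, muscle and nerve function. Bilateral MRI and both strength tests are listed at ET, with the MRI waived only for withdrawals who had one within 4 weeks. Adverse events are collected at ET and EOS. This stands and keeps the point small; what is missing is the dedicated examination.

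Third, the age of the pregnancy test on a dosing day is not a q8w weakness. The two arms test on the same six days through Day 505, and on the q4w doses of Days 309, 477 and 645 the last test is older still (309 − 169 = 477 − 337 = 645 − 505 = 140 days). This is correct: the arms differ by exactly one test, the one at ET. The ages above show only what a q8w withdrawal leaves with when that test is absent.

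Fourth, an exit test cannot prevent exposure, contraception counselling continues to EOS, and pregnancies must be reported during the study and for 8 weeks after the last dose (Section 13.6). For a q8w completer that 8-week window closes on the ET day, which might be a reason to omit the test. It cannot be the reason for an early withdrawal, for whom the window may be wide open. The test's value lies in detection and follow-up.

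The q4w omission matters little: the examination comes 28 days later, and the results are only listed (Section 14.2.5).

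**Conclusion.** The concern holds and is minor. Three ET cells differ between Tables 9 and 10 without explanation, and the two q8w omissions leave a small safety gap at exit. For completers that is 1 of 12 injections without a later dedicated site examination and 3 of 12 doses without a later pregnancy test, against 0 of 24 for both in q4w. The clearest case is a q8w subject who withdraws shortly after an injection. The q4w omission is a matter of consistency. The Day 169 muscle-volume analysis is not affected.

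The counts assume planned visit days without windows or delays. They also assume that the tables, which were read from PDF text, are complete. The intact row lengths rule out a shifted column but not a lost mark, so the sponsor should confirm the three cells against the original. The Study Manual might add procedures at ET; it was not available.

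**What to change.** In Appendix 1, mark the injection-site examination and the urine pregnancy test (for women of childbearing potential) in the ET column of Table 10, and the limited physical examination in the ET column of Table 9. Through Sections 9 and 13.5, completers and early withdrawals in both arms would then have the same ET safety set. If any of the differences is intended, a footnote should give the reason and say what applies to early withdrawals.

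The cost is one brief site examination and one urine test per q8w subject as applicable, and one limited physical examination per q4w subject. All are existing study procedures at a visit that already takes place. The muscle-volume analysis does not change.
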